***Recruitment***

Potential participants will be identified as inpatients or in new patient clinics of the adult cardiac surgeons in the Division of Cardiothoracic Surgery, Department of Surgery, Washington University School of Medicine. Patients will be introduced to the study at the preoperative consultation visit, at which point they will be invited to participate and provide informed consent if they agree to join the study. Potential subjects will have at least 48 hours, typically longer and up until the time of surgery to consider participation and may take the consent home to discuss with friends and family, if they so choose. They will have ample time to ask questions of the surgeon prior to agreeing to participate. Upon providing informed consent, the subject will be considered enrolled into the study.

***Peri-operative period***

Troponins will be drawn in the operating room prior to initiation of cardiac surgery and post-operatively upon arrival to the ICU, 12 hours, and 24 hours.

Subjects will undergo their standard of care, planned cardiac surgery procedure as directed by their treating surgeon.

Given that our primary endpoint is transfusion requirement, we will assess this need throughout the entire peri-operative period. Standard blood draws after surgery to evaluate hematocrit will be used for analysis. We will use the electronic medical records to obtain this information.

***Post-Operative Follow-Up***

There is no active participation for subjects beyond the 24 hour troponin and hematocrit collection time points. Health information on post-operative complications, should they occur, will be collected until the patient is discharged from the hospital. Data on vital status will be collected from the subject's medical record at the time of the standard of care 30-day post-operative visit with the surgeon.

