## 1.0 INTRODUCTION AND BACKGROUND

Cardioplegia was first introduced as a method to protect the heart during cardiac surgery in the 1950s (1). Initially, it consisted of a crystalloid solution and in the 1970s Follette and colleagues proposed that blood was the best mode of delivery of cardioplegia as it is rich in nutrients and oxygen (2). Blood has better osmotic, buffering, and antioxidant qualities that are needed by ischemic myocardium. More recent studies comparing blood and crystalloid cardioplegias showed that there was less cardiac edema, and recovery of ventricular function was more rapid with blood based cardioplegia (3). A meta-analysis of over 5000 patients corroborated these findings and showed that blood based cardioplegia reduced the incidence of postoperative low cardiac output syndrome and was associated with less myocardial damage (4).

Standard diluted blood cardioplegia can also be modified to undiluted blood cardioplegia also known as microplegia. To compare the cardioprotection of 4:1 blood:crystalloid cardioplegia to microplegia, McCann et al randomized 20 pigs to either group. Cardiac edema was measured using histologic morphometrics and echocardiogram. It was noted that both edema percentage and left ventricular mass were significantly more decreased in the microplegia group. Furthermore, all animals receiving microplegia were successfully weaned off cardiopulmonary bypass, whereas only 40% of those receiving standard cardioplegia were successfully weaned (5).

More recently, Algarni *et al.* showed decreased prevalence of low cardiac output syndrome in patients who received microplegia (n=2,630) (6). Another study compared microplegia and standard cardioplegia in patients undergoing coronary artery bypass grafting and found that the microplegia group had lower troponin levels during the post-operative course. Moreover, microplegia resulted in lower transfusion rates and decreased length of hospital stay (7).

A high rate of patients undergoing cardiac surgery require red blood cell transfusions (RBC). Red blood cell transfusions are strongly associated with both infection and ischemic postoperative morbidity, length of stay, increased early and late mortality, and overall hospital costs (8). Given that previous studies have shown that microplegia is associated with less transfusions, it would be reasonable to incorporate this into practice at Washington University.

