### **5.0 STUDY DESIGN**

The hypothesis will be accomplished in a randomized, blinded, prospective institutional study conducted at two sites, Barnes Jewish Hospital and Christian Northeast Hospital. 314 patients will be randomized to either receive diluted 4:1 cardioplegia or nondiluted microplegia. This will be a blinded study to both the patient and surgeon. The patient will be randomized during the preoperative period. Quest Medical Inc. will supply us with the microplegia MPS-2 machines needed to conduct this study. Outcomes will be measured by a blinded clinician.

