## **9.0      STATISTICAL ANALYSIS**

Continuous variables will be expressed as mean  $\pm$  standard deviation or as median with range. Categorical variables will be expressed as frequencies and percentages with outcomes compared using the  $\chi^2$  or the Fisher exact test. Continuous outcomes will be compared using the *t* test for means of normally distributed continuous variables and the Mann-Whitney U nonparametric test for skewed distributions. Significant covariates on univariate analysis ( $p \leq 0.10$ ) or covariates deemed clinically relevant based on experience will be entered into a multivariate binary logistic regression analysis.

A sample size of 314 patients will be randomized to either receive standard 4:1 cardioplegia or microplegia. The sample size was calculated based on a one tailed test with alpha 0.05 and beta 0.2 (80% power) to detect a 25% relative risk reduction in pRBC units transfused. An interim analysis will be completed following the enrollment of 150 patients.

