## 15.0 Appendix 3: Data Collection

**Table 1:** Baseline pre-operative, operative, and post-operative variables to be examined.

Pre-operative variables	Intra-Operative Variables	Post-Operative Variables
Age	pRBC transfusion (see appendix 2, peri-operative transfusion form): date, number of units, name of staff ordering transfusion, actual/predicted hematocrit, justification if hematocrit >20%	pRBC transfusion (see appendix 2, perioperative transfusion form): date, number of units, name of staff ordering transfusion, hemoglobin level, justification if hemoglobin $\geq 7.0$ g/dL.
Weight	Platelet transfusion: number of units	Platelet transfusion: number of units
Dyslipidemia	FFP transfusion: number of units	FFP transfusion: number of units
Hypertension	Mortality	Hematocrit on arrival to ICU
COPD	Clamp time	Hematocrit 24 hours post-operatively
Coronary artery disease	Amount of cardioplegia/microplegia delivered	30 day mortality
Liver disease	Type of surgery	Time on ventilator
Cerebrovascular disease	CPB time	Hours in the intensive care unit
Previous cardiac interventions	Cross-clamp time	Length of hospital stay
History of arrhythmia	Cardioplegia technique	Renal failure
Diabetes mellitus	Number of grafts	Pulmonary complications
LVEF (%)	Concomitant procedures	Low output syndrome
Congestive heart failure	Pre-CPB hematocrit	Myocardial infarction
Peripheral vascular disease	On-CPB hematocrit	Serial troponins: arrival to ICU, 12 and 24 hours post-op
Hemoglobin, hematocrit	Post-CPB hematocrit	New onset post-op atrial fibrillation
Creatinine	Date of surgery	Stroke
Troponin	Skin incision to skin close time	Mortality
Previous PCI +/- stents	Cardioplegia Delivery	Readmission
Angina	Additive Volume	Readmission date
BMI	Arrest Agent Volume	Readmission reason
Height	Total CDPG	
Ethnicity	Crystalloid Amount	
Race	Crystalloid Total	
Chronic Lung Disease	Anesthesiologist	
Immunocompromise	Perfusionist	
Mediastinal Radiation	Starting glucose	

Thoracic Aorta Disease	Final glucose	
Sex	TEE score	
Date of admission	Time to arrest	
	Volume to arrest	
	Cryoprecipitate volume	Cryoprecipitate volume

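### Complications are counted only to discharge, so observation time may differ by arm; readmission has no stated window, and 30-day vital status has no later check

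*Combined protocol and SAP*

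**What the plan says.** - **Complications.** Section 5.0, Post-Operative Follow-Up: "Health information on post-operative complications, should they occur, will be collected until the patient is discharged from the hospital". Aim 2 in Section 2.0 refers to the peri-operative period and gives no end day.
- **Vital status.** Same section: "Data on vital status will be collected from the subject's medical record at the time of the standard of care 30-day post-operative visit". Active participation ends with the 24-hour blood samples.
- **Readmission.** Appendix 3, Table 1 lists readmission, "Readmission date" and the reason among the post-operative variables. Neither the table nor Section 5.0 says over what period readmissions count.
- **Length of stay.** It is a post-operative variable in Table 1. In Section 1.0 the background reports, from a study in coronary bypass patients, that "microplegia resulted in lower transfusion rates and decreased length of hospital stay".
- **Analysis.** Section 9.0 compares categorical outcomes as proportions by chi-square or Fisher exact test. It names no time-to-event method and no rule for missing outcomes.

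**The concern.** A proportion of patients with a complication is comparable between arms only if both arms are watched for the same length of time. Here each patient is watched for as long as the hospital stay lasts, and the plan's own rationale suggests that treatment may shorten the stay. If the microplegia arm goes home sooner, complications that would have occurred on the days saved are not counted in that arm. It can then look better on morbidity with no true effect, and in the direction of the hypothesis.

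Two smaller gaps sit beside this. Without a window, the period for counting readmissions could be chosen after the data exist. And a patient with no record entry by the 30-day visit has no defined route to a 30-day vital status.

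**Working it through.** **1. Is there a plan figure to reproduce?** Not for this point. The only sample-size figure is 314, set for the primary endpoint "to detect a 25% relative risk reduction in pRBC units transfused". It cannot be reproduced, because no control rate, mean or SD is given. It is used below only for arm size: 314 / 2 = 157, assuming 1:1 allocation, which the documents do not state.

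**2. What could unequal windows do?** The documents give no complication hazard and no length of stay, so every input in this step is an assumption. Both arms have the same true hazard. Every patient in an arm stays the same number of days: 7 v 6, or 8 v 6.

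*Constant daily hazard h:* P(counted by discharge) = 1 − exp(−h × stay).

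| h per day | Stay (days) | Longer stay | Shorter stay | Difference (points) | Apparent RR |
|---|---|---|---|---|---|
| 1% | 7 v 6 | 6.8% | 5.8% | 0.9 | 0.86 |
| 3% | 7 v 6 | 18.9% | 16.5% | 2.5 | 0.87 |
| 1% | 8 v 6 | 7.7% | 5.8% | 1.9 | 0.76 |
| 3% | 8 v 6 | 21.3% | 16.5% | 4.9 | 0.77 |

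*Front-loaded hazard, 20% affected by day 30, time constant m:* P = 0.20 × (1 − exp(−stay/m)) / (1 − exp(−30/m)).

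| m (days) | Stay (days) | Longer stay | Shorter stay | Difference (points) | Apparent RR |
|---|---|---|---|---|---|
| 2 | 7 v 6 | 19.4% | 19.0% | 0.4 | 0.98 |
| 5 | 7 v 6 | 15.1% | 14.0% | 1.1 | 0.93 |
| 2 | 8 v 6 | 19.6% | 19.0% | 0.6 | 0.97 |
| 5 | 8 v 6 | 16.0% | 14.0% | 2.0 | 0.88 |

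With a fixed 30-day window the two arms would have identical proportions (RR 1.00) in every row.

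**3. Effect on a test.** Rejection probability = Φ((d − 1.645 × SE0) / SE1), where d is the difference in proportions, SE0 is its pooled and SE1 its unpooled standard error, and n = 157 per arm. The level is one-sided 0.05, as in the sample-size statement; Section 9.0 does not give the sidedness of the complication tests. Against a nominal 5%:

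- constant hazard of 1 to 3% per day: 10 to 14% for 7 v 6 days, 16 to 29% for 8 v 6 days;
- front-loaded, m = 2 to 5 days: 6 to 9% for 7 v 6 days, 7 to 12% for 8 v 6 days.

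**4. Readmission.** The choice of window changes what is counted. For assumed discharge on day 6 or day 8, a window to day 30 after surgery leaves 30 − 6 = 24 or 30 − 8 = 22 days at risk. A window of 30 days after discharge runs to day 36 or day 38, later than the record check timed to the 30-day visit. The plan chooses neither.

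**5. Vital status.** Bounds for one arm: deaths / 157 up to (deaths + unknown) / 157. With an assumed 3 known deaths, 3/157 = 1.9%. If status is unknown for 3, 8 or 16 patients (about 2%, 5% and 10%), the upper bound is 6/157 = 3.8%, 11/157 = 7.0% or 19/157 = 12.1%. Because deaths are few, even modest missingness can match or exceed them.

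**The case against.** Several points on the other side are sound.

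- **Visit-only vital status.** A reader might infer that 30-day status is obtained only from patients who attend. The text does not support this. The medical record is the source and the visit sets the timing, so a recorded death counts without attendance. Table 1 also has separate intra-operative and post-operative mortality items. What remains is the patient with no record entry by that time.
- **A contradiction on readmission.** One might also read Section 5.0 as restricting post-discharge data to vital status, against Table 1. It contains no such restriction; it is silent on readmission, and Section 6.0 sends the reader to Table 1 for the full list. Since dates of surgery and readmission are both collected, a common window can be applied. It only needs to be stated in advance.
- **Bias as established fact.** The shorter stay comes from one cited study in coronary bypass patients, with no size given, whereas this trial takes non-emergent cardiac surgery generally. Patient and surgeon are blinded, so knowledge of allocation should not drive discharge. Complications also prolong stay: if microplegia shortens stay by preventing them, the difference is real. The calculation above treats stay as independent of complications, and with early complications the effect is small.
- **Reach.** Troponins have fixed times. Ventilator time, ICU hours and length of stay are not affected in this way, and nothing here shows an effect on the primary transfusion endpoint.
- **Design choice.** In-hospital complications with 30-day mortality is a coherent design, and post-discharge capture through one record system would be incomplete too.

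These points limit the concern to complications, readmission and a small part of vital status. They do not remove it. Blinding does not equalise stay if treatment speeds recovery, and a plain comparison of in-hospital proportions cannot separate fewer complications from less time in which to observe them.

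**Conclusion.** The point holds as a conditional risk and a cheap improvement, not as a demonstrated flaw. Complication counting ends at an event that treatment may bring forward, and the planned analysis makes no allowance for it. If stay differs by arm, the comparison could favour the arm discharged sooner.

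The size cannot be derived from the documents. Under the assumed stays and equal hazards, the spurious difference runs from 0.4 points (RR 0.98) with early complications to 4.9 points (RR 0.77) with a constant 3% daily hazard. If stay does not differ, this problem does not arise.

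The readmission gap rests on the text alone: no window is stated. The vital-status gap is narrow, being patients without a record entry by the 30-day visit, for whom there is neither a later check nor a missing-data rule.

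**What to change.** Amend Section 5.0, Post-Operative Follow-Up, as follows:

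1. Count complications and readmission to day 30 after surgery for every randomised patient. Use the record review already made around day 30 and the readmission date and reason already collected.
2. Report in-hospital complications as a supporting count.
3. Repeat the record check for any patient with no documented contact on or after day 30.

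The cost is protocol wording, a somewhat longer look at a record already being opened, and a second look for a few patients. No new patient contact is needed. A telephone call would add contact and staff work, and the point does not depend on it. The downside is that events treated outside the record system may be incompletely captured after discharge, which is why the in-hospital count should stay alongside.

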**6.0 OUTCOME MEASURES (DATA)**

Data will be obtained from the electronic medical record system at Washington University. Study staff from each participating site will review the subject's medical record and obtain the study-specific data to include but is not limited to the following. For a complete list of all data variables to be collected please see table 1. The study-specific data will be collected by the study staff and entered into a REDCap database that will be created specifically for this study. REDCap is a mature, secure web application for building and maintaining databases (<https://redcap.wustl.edu>).

Electronic study data will be entered in a secure REDCap database. Only investigators and the study team for this study will have access to the study data. They will each use a unique log-in ID and password that will be kept confidential.

See Appendix 3: Data Collection for Table 1

**7.0 RISKS**

All microplegia will be delivered using the MPS-2 Myocardial Protection System. This is an approved device currently used in many cardiac centers worldwide. There is no change in risk that can be associated with the use of microplegia versus standard cardioplegia currently used as standard of care.

Blood drawing poses the following risks: pain, bleeding, or bruising and rarely, infection. All peri-operative blood draws can be performed while the subject has a standard of care intravenous line in place. There will be no needle sticks required.

There is a rare risk of breach of confidentiality of study data.

## **8.0      BENEFITS**

There are no known direct benefits to subjects; however, there will be an improved understanding of cardioplegia techniques and possibly improved outcomes of cardiac surgery patients.

## **9.0      STATISTICAL ANALYSIS**

Continuous variables will be expressed as mean  $\pm$  standard deviation or as median with range. Categorical variables will be expressed as frequencies and percentages with outcomes compared using the  $\chi^2$  or the Fisher exact test. Continuous outcomes will be compared using the *t* test for means of normally distributed continuous variables and the Mann-Whitney U nonparametric test for skewed distributions. Significant covariates on univariate analysis ( $p \leq 0.10$ ) or covariates deemed clinically relevant based on experience will be entered into a multivariate binary logistic regression analysis.

A sample size of 314 patients will be randomized to either receive standard 4:1 cardioplegia or microplegia. The sample size was calculated based on a one tailed test with alpha 0.05 and beta 0.2 (80% power) to detect a 25% relative risk reduction in pRBC units transfused. An interim analysis will be completed following the enrollment of 150 patients.

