**Intraoperative:**

1. It is appropriate to transfuse if predicted hematocrit on cardiopulmonary bypass <20% or actual hematocrit on cardiopulmonary bypass falls below 20%.

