**Postoperative:**

1. It is appropriate to transfuse if hemoglobin falls below 7 g/dL
2. It is appropriate to transfuse if hemoglobin falls below 8 g/dL and any of the following are present:
  - patient has borderline hemodynamics, or has become dependent upon pressors/inotropes
  - patient is symptomatic (i.e. dizziness, lightheadedness, unable to ambulate)
  - patient is in acute renal failure
3. It is appropriate to transfuse in any case of ongoing hemorrhage/acute blood loss

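### Fixing pre-operative hematocrit and weight in advance as covariates in the pRBC-units comparison would gain precision at no cost; Section 9.0 guarantees neither a place

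*Combined protocol and SAP*

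**What the plan says.** **Endpoint and sizing.** Section 5.0 (Peri-operative period) says: "Given that our primary endpoint is transfusion requirement, we will assess this need throughout the entire peri-operative period". It does not say whether that means any transfusion or the number of units. Section 9.0 sizes the trial at 314 patients, one-tailed alpha 0.05 and 80% power, to "detect a 25% relative risk reduction in pRBC units transfused". It gives no control-arm rate, mean or standard deviation.

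**Tests.** Section 9.0 assigns categorical outcomes to the chi-square or Fisher test. Continuous outcomes go to a t test or the "Mann-Whitney U nonparametric test for skewed distributions". No test is tied to the primary endpoint by name. The next sentence plans a multivariable binary logistic regression, with covariates entering if univariate p ≤ 0.10 or if experience suggests they matter. Its outcome, its covariates and its role (primary or supportive) are not named. Section 5.0 describes no stratification of the randomization.

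**Baseline data and triggers.** Table 1 (Appendix 3) lists "Hemoglobin, hematocrit", weight, height and BMI among the pre-operative variables. Appendix 1 ties transfusion to thresholds. During surgery these are predicted hematocrit below 20% or "actual hematocrit on cardiopulmonary bypass falls below 20" per cent. After surgery: "It is appropriate to transfuse if hemoglobin falls below 7 g/dL", with further criteria for other situations.

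**The concern.** The hypothesis in Section 2.0 is that diluted cardioplegia raises transfusion rates, and the transfusion rules are hematocrit and hemoglobin thresholds. A patient's starting hematocrit sets the distance to the threshold, and body size plausibly affects how far a given fluid volume dilutes the patient. On the protocol's own logic, both should predict units transfused.

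Eligibility covers most non-emergent adult cardiac surgery, so both variables are likely to vary widely. If neither is in the model for units, the variation they explain stays in the error term. A chance difference between arms in either one then passes into the estimated effect. The data are already being collected, so this precision needs no further patients.

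**Working it through.** **1. The plan's own figure.** With no control rate, mean or SD, 314 cannot be reproduced forward. It can be solved backward, assuming 1:1 allocation (157 per arm) and no dropout.

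- *Units as a mean:* n per arm = 2 × (SD/mean)² × (1.645 + 0.842)² / 0.25². With SD/mean = 0.89 this is about 157, so N = 314.
- *Any transfusion, yes/no:* 56% against 0.75 × 56% = 42%, one-sided and without continuity correction, also gives N = 314.

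Both readings fit, so the sample size does not settle which endpoint is meant.

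**2. Gain from adjustment, starting from the stated 80% power.** If baseline covariates explain a share R² of the variance in units, the standard error shrinks by √(1 − R²):

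- power = Φ((1.645 + 0.842)/√(1 − R²) − 1.645)
- equivalent unadjusted N = 314/(1 − R²)

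| R² (assumed) | Power | Equivalent unadjusted N |
|---|---|---|
| 0 | 80% | 314 |
| 0.05 | 81.8% | 331 |
| 0.10 | 83.5% | 349 |
| 0.20 | 87.2% | about 393 |
| 0.30 | 90.8% | 449 |

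**3. Simulation at the protocol's 25% reduction.** Assumptions: gamma-Poisson counts, control mean 2 units, dispersion 0.8, 157 per arm, one-sided 0.05, two baseline covariates.

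| R² on ranks | Unadjusted power | Adjusted power | Gain (points) |
|---|---|---|---|
| 0.03 | 59.2% | 60.1% | 0.9 |
| 0.09 | 55.0% | 57.7% | 2.7 |
| 0.20 | 46.4% | 52.5% | 6.1 |

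A repeat of this set-up put the gain at about 1 to 7 points. A separate simulation used one covariate, dispersion 0.5 or 1.0, and R² from about 0.05 to 0.24. There, rank-based covariance analysis gained about 1 to 10 points over Mann-Whitney, and ordinary covariance analysis about 1 to 11 over the t test. With no treatment effect, rejection was about 3% to 6% for adjusted and unadjusted tests alike, consistent with 5%.

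Unadjusted power in the table is below 80% because the assumed counts are more variable than 314 allows for. Their variance is 2 + 0.8 × 2² = 5.2, so SD/mean = √5.2/2 = 1.14 before the covariates add spread, against 0.89 in step 1.

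**4. Chance imbalance.** The standardized baseline difference has SE √(2/157) = 0.113. A difference of at least 0.2 SD in either direction therefore occurs in about 7.6% of trials. For a single covariate with R² = 0.20, it shifts the unadjusted estimate by √0.20 × 0.2 = 0.089 SD. The design effect is (1.645 + 0.842) × 0.113 = 0.281 SD, so the shift is about 32% of it. Given that imbalance in microplegia's favour, the one-sided error is 1 − Φ((1.645 × 0.113 − 0.089)/(0.113 × √0.80)), about 17%. Averaged over all randomizations it remains 5%.

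**The case against.** The strongest reply is that Section 9.0 does plan an adjusted analysis. Hemoglobin and weight could enter the logistic regression on clinical grounds without passing the p ≤ 0.10 screen. If the endpoint is any transfusion, that model could correct an imbalance. This stands, so a reader who infers that the plan has no adjustment, or that imbalance must go uncorrected, goes further than the text. It does not close the gap: a binary model cannot analyse units, and its outcome, role and covariates are open.

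Two further points stand. First, calling the primary comparison unadjusted is an inference, because no test is assigned to the primary endpoint and the sizing sentence mixes relative risk with units. It is the natural reading only if the endpoint is units. Under a yes/no endpoint the R² formula does not apply directly. Second, the covariates do not determine transfusion. Appendix 1 also accepts ongoing hemorrhage and hemodynamic, symptomatic and renal criteria, and it allows justified deviations. R² could therefore be low, and at 0.05 the gain is only about 2 points.

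An unadjusted comparison in a randomized trial is also valid. A reader might take the imbalance figures to mean an inflated error rate. They do not: the 17% is conditional on one particular imbalance.

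**Conclusion.** The point holds as a free improvement. For pRBC units, Section 9.0 provides only unadjusted tests, and nothing guarantees that pre-operative hemoglobin/hematocrit or body size enters any model. The cost is precision and protection against a chance imbalance; overall type I error is preserved.

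The size rests on an R² that the documents do not give. The gain runs from about 2 to 11 points on the stated 80% power for R² of 0.05 to 0.30, and from about 1 to 7 points in the dispersion-0.8 simulations, where unadjusted power was about 46% to 59%. Those lower powers might be read as showing that the trial is underpowered. They do not, because they follow from an assumed mean and dispersion. Equally, adjustment would not restore 80% power if the counts are that variable.

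**What to change.** In Section 9.0, state that the primary comparison of pRBC units uses one adjusted analysis suited to counts, for example a negative-binomial model or a rank-based covariance analysis. Enter pre-operative hematocrit (or hemoglobin) and weight as continuous covariates, fixed in advance and exempt from the p ≤ 0.10 screen. Keep the unadjusted test as a supportive analysis.

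If the primary endpoint is confirmed as any transfusion, name the logistic model as the primary analysis with the same fixed covariates. In either case, state the logistic model's outcome and role.

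Make the change before the interim analysis at 150 patients, so that the covariates are not chosen after sight of results by arm. The cost is one or two sentences, with no new data, visits or patients.

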## 2.0 HYPOTHESIS AND AIMS

The hypothesis is that diluted 4:1 cardioplegia used in adult cardiac surgery at Washington University in St. Louis contributes to increased transfusion rates peri-operatively and incorporation of Quest, Inc. microplegia may decrease RBC transfusion rates, and thus, impact overall morbidity and mortality after cardiac surgery.

Specific aims are:

1. To determine if use of microplegia results in less peri-operative transfusions compared to diluted 4:1 cardioplegia.
2. To investigate the effects of microplegia on overall morbidity and mortality during the peri-operative period. We will assess operative mortality and 30 day mortality. We will examine intra-operative and post-operative complications. A complete list of variables to be examined can be found in table 1. We will determine if microplegia results in better myocardial protection than standard cardioplegia by assessing pre-operative, intra-operative and post-operative serum troponin levels.

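### Troponin, the stated measure of myocardial protection, has no named time point or summary and no adjustment for the pre-surgery value that is already collected

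*Combined protocol and SAP*

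**What the plan says.** Section 2.0 (Aim 2) states that better myocardial protection will be determined by "assessing pre-operative, intra-operative and post-operative serum troponin levels". No other measure is named for that question.

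Section 5.0 (Peri-operative period) sets the sampling: "Troponins will be drawn in the operating room prior to initiation of cardiac surgery", and then "post-operatively upon arrival to the ICU, 12 hours, and 24 hours". No subset of patients is specified. Table 1 in Appendix 3 lists troponin among the pre-operative variables and, among the post-operative ones, "Serial troponins: arrival to ICU, 12 and 24 hours post-op".

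Section 9.0 has one rule for every continuous outcome: a t test if the data are normally distributed, otherwise the "Mann-Whitney U nonparametric test for skewed distributions". Covariates that reach p ≤ 0.10 on univariate analysis, or that are judged clinically relevant, "will be entered into a multivariate binary logistic regression analysis". Section 9.0 does not mention troponin. It gives no analysis of covariance, change from baseline, repeated-measures model, or choice of time point or summary.

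**The concern.** There are two gaps. First, with three post-operative values per patient and no named contrast, the quantity that answers the protection question can be chosen after the data are seen: one time point, the peak, the area under the curve, an average, or a t test versus a rank test.

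Second, a pre-surgery value is scheduled but the plan does not use it in the comparison. Where baseline and later troponin are correlated, leaving baseline out widens the confidence interval. Any chance difference between arms at baseline also carries over into the post-operative comparison in proportion to that correlation. The covariate sentence in Section 9.0 does not close this gap, because a binary logistic model has no place for a continuous outcome.

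What is at stake is the precision and credibility of a secondary conclusion, not the primary transfusion result.

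**Working it through.** **The plan's own figure.** Section 9.0 gives 314 patients for the transfusion endpoint and no figure for troponin. The 314 cannot be reproduced from the stated inputs, because no control rate, mean or SD is given. It does not bear on this point beyond setting the number of patients.

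**Inputs**
- Total 314 (Sections 5.0 and 9.0). The allocation ratio is not stated, so 1:1 is assumed: 157 per arm.
- Two-sided 0.05 and 80% power (assumption). The only alpha in the plan is one-sided 0.05, for the transfusion endpoint; that version is shown below.
- Correlation r between baseline and post-operative troponin on the log scale: not in the documents, so shown as a range from 0.
- One post-operative time and complete samples (assumption).

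**Unadjusted detectable difference**

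(1.960 + 0.842) × √(2/157) = 2.802 × 0.1129 = 0.316 SD

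**After adjustment for baseline.** The residual variance is multiplied by 1 − r², so:
- detectable difference = 0.316 × √(1 − r²)
- equivalent N = 314/(1 − r²)
- power at 0.316 SD = Φ(2.802/√(1 − r²) − 1.960)

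| r | SE reduction | Detectable difference (SD) | Equivalent N | Power at 0.316 SD |
|---|---|---|---|---|
| 0 | 0% | 0.316 | 314 | 80.0% |
| 0.2 | 2.0% | 0.310 | 327 | 81.6% |
| 0.3 | 4.6% | 0.302 | 345 | 83.6% |
| 0.5 | 13.4% | 0.274 | 419 | 89.9% |
| 0.6 | 20.0% | 0.253 | 491 | 93.8% |

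Example at r = 0.5: 2.802/0.866 − 1.960 = 1.276, and Φ(1.276) = 89.9%.

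With the plan's one-sided 0.05, the unadjusted detectable difference is 0.281 SD. Power at that difference after adjustment is 81.4%, 83.2%, 89.0% and 92.8% at r = 0.2, 0.3, 0.5 and 0.6.

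**Simulation check** (4,000 runs per correlation, normal data as for log troponin, two-sided 0.05). Covariance adjustment gave 80.0%, 81.5%, 83.9% and 89.8% power at r = 0, 0.2, 0.3 and 0.5. The t test stayed near 80% and Mann-Whitney near 78%. A t test on change from baseline gave 51%, 59%, 66% and 80%, so a simple change score is no substitute when the correlation is low.

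**Chance imbalance.** If baseline differs between arms by k standard errors, the unadjusted difference shifts by r × k × √(2/157). For k = 1.96 that is 0.044, 0.066 or 0.111 SD at r = 0.2, 0.3 or 0.5. Given such an imbalance, the two-sided type I error of the unadjusted test is

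1 − Φ((1.96 − rk)/√(1 − r²)) + Φ((−1.96 − rk)/√(1 − r²)),

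which is 6.3%, 7.9% or 12.9%. For k = 1 it is 5.0%, 5.0% or 4.8%, so only an unusually large imbalance matters for a two-sided test.

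**The case against.** The strongest reply is that nothing here is an error. In a randomised comparison the unadjusted t and Mann-Whitney tests are valid, and averaged over randomisation they are unbiased. That stands. A reader might infer that the troponin comparison is biased, or that a baseline imbalance passes through in full. Neither follows: only the correlation-weighted part carries over, and the loss is one of efficiency and of the result given an observed imbalance.

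The size of the gain is also uncertain, and this stands too. The documents give no correlation. Entry is limited to non-emergent surgery without pre-operative mechanical support, so baseline values may be low and weakly informative; at r of 0.3 or below the standard error falls by less than 5%. Inpatients are recruited and raised troponin is not an exclusion, so a reader might infer that baseline must be informative. The documents allow that but do not establish it.

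A reader might also infer that Section 9.0 commits the trial to three separate troponin tests, one per time. It does not. It gives a generic rule and is silent on how the serial values are to be used. The supportable statement is that the troponin endpoint is unspecified.

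Finally, the power figures describe a single time point. The variance of an average over three times also depends on the within-patient correlation, so the table is a guide to the value of the baseline covariate and not the exact gain from the model proposed below.

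None of this defends leaving the time point or summary unnamed, or leaving a scheduled baseline out of the comparison.

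**Conclusion.** The point holds as a low-cost improvement to a secondary analysis. Section 9.0 leaves the troponin endpoint undefined and provides no model that can use the pre-surgery sample. With 157 per arm, two-sided 0.05 and one post-operative time, adjustment would raise 80% power to between 80% (correlation 0) and 94% (correlation 0.6). The gain is small up to about 0.3 and material from about 0.5. At correlation 0 adjustment costs essentially nothing (simulated power 80.0% against 79.8% for the t test). The case for naming one contrast in advance does not depend on the correlation at all.

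There is also a minor wording conflict. Aim 2 refers to an intra-operative level, but the only sample that Section 5.0 schedules in the operating room is the one taken before surgery starts, and Table 1 lists no other.

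**What to change.** In Section 9.0, before any troponin data are compared by arm (including at the interim analysis after 150 patients):

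1. Analyse log troponin at ICU arrival, 12 h and 24 h in one repeated-measures model with arm, time, arm-by-time, log pre-surgery troponin and site.
2. Name one contrast as the troponin result, for example the average arm difference over the three times. Another summary is acceptable if it is fixed in advance.
3. Report the ratio of geometric means with its 95% confidence interval.
4. State how values below the detection limit are handled before taking logs, and how a missing pre-surgery sample is handled.
5. Reconcile the intra-operative wording in Aim 2 with the sampling schedule, either by removing it or by saying that it means the pre-surgery sample drawn in the operating room.

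The cost is analysis-plan wording and routine model code. All four samples are already scheduled, so no extra blood draw, patient or data item is needed.
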